2 BACKGROUND INFORMATION AND SCIENTIFIC RATIONALE

2.1 Background Information

[figure not shown]
The three major soil transmitted helminthes, *Ascaris lumbricoides* (roundworm), *Necator americanus/Ancylostoma duodenale* (hookworms) and *Trichuris trichiura* (whipworm) are among the most prevalent parasites worldwide. They are highly prevalent in developing countries that suffer from poverty and poor sanitation. It is estimated that these three helminthes have an overall prevalence of one billion cases worldwide. Nearly half of these cases result in significant morbidity especially affecting young children (1). Current control measures require the periodic administration of one of the four antihelminthics: mebendazole, albendazole, levamisole or pyrantel. Of these drugs, the benzimidazoles (mebendazole and albendazole) are the most frequently used antihelminthics. However, these drugs show varying efficacy against the array of human helminthes. Single oral doses of these compounds are highly effective against *Ascaris lumbricoides*, but have significantly less efficacy for hookworms and *Trichuris trichiura* (2).

Oxfendazole (OXF) is a potent, broad-spectrum antihelminthic drug that is approved and marketed for veterinary use. Oxfendazole is currently marketed for use against lungworms and enteric helminthes in beef livestock. In humans, current benzimidazoles include albendazole and mebendazole. Though all of the benzimidazoles show chemical similarities, the compound oxfendazole reaches peak blood levels more slowly following absorption from the intestinal tract than many other benzimidazoles, thereby maintaining effective concentrations for a longer time in both the serum and intestinal tract. This prolonged half-life is attractive for pursuing single dose therapy for certain helminthes including uncomplicated cysticercosis. However, even with this more prolonged half-life it is likely that extended therapy will likely be required for the soil transmitted helminthes such as *Trichuris trichiura* and hookworm infections. Given the potentially favorable pharmacokinetics, oxfendazole is an attractive compound for transition to human use and animal and human studies outlined below have begun to define the safety and pharmacokinetic parameters of this compound.

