2.1.2 Human Phase I Safety and Pharmacokinetics

A recent dose escalation study has been performed evaluating 70 healthy adult men and women of non-child bearing potential who were age 18-45 (NCT02234570, DMID 12-0053, unpublished). Seven dose groups were studied (0.5, 1, 3, 7.5, 15, 30 and 60 mg/kg) and each dose group was comprised of 10 subjects of whom eight received study drug and two received placebo. All subjects received a single dose of study drug or placebo and were followed for 14 days for safety and the pharmacokinetics of oxfendazole and metabolites including fenbendazole and oxfendazole sulfone were evaluated in blood and urine. There were no study drug associated serious adverse events identified. Sixteen unsolicited adverse events were experienced by 10 subjects. Six were considered related to the study treatment. Five of the events were mild and included one subject with an increased PR interval 14 days following the dose of study drug, and the remaining events were gastrointestinal events (nausea, loose stools, intestinal gas, and diarrhea, all of which occurred in the 30 or 60 mg/kg dose groups. There was one event, a sore throat that was considered moderate in intensity. Mild to moderate laboratory events were seen in hematology and chemistry tests. There were no patterns identified related to timing of the abnormal laboratory studies or dose of oxfendazole and the placebo group had similar rates of abnormal laboratory values.

The median time of maximum concentration (T_{max}) occurred at 2 hours and the geometric mean maximum concentration (C_{max}) ranged from 943.9-6768.4 ng/mL. The exposure was non-linear, plateauing at 15 mg/kg. The half-life ($t_{1/2}$) was consistent between groups and ranged from 8.5-11 hours. The overall fraction of drug excreted in the urine was very low and the geometric mean AUC_{0-t} for the sulfone metabolite was 11.5-15% of oxfendazole AUC_{0-t} while fenbendazole AUC_{0-t} was less than 1% of oxfendazole AUC_{0-t} for each dose group.

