- Fasting (water is permitted) subjects will remain fasting (water is permitted) for two hours after the administration of drug.
- Fed subjects will receive a high fat breakfast. Approximately 30 minutes (+/- 15 minutes) following completion of the meal, the study nurse will administer a single 3 mg/kg oral dose of oxfendazole.
- Lunch and dinner will be provided. Subjects will be allowed to eat snacks but will be asked to avoid drinking grapefruit juice and excessive (>2 cups) coffee.
- 10 mL of blood for oxfendazole level will be drawn at 30 minutes, 1, 2, 3, 4, 6, 9, and 12 hours (all times have a window of +/- 15 minutes except the 9 and 12 hour samples which have a window of +/- 30 minutes- it is critical to record the exact time of blood draw).
- Perform EKG approximately 2 hours following study drug (+/- 20 minutes)
- Assess AEs and SAEs throughout the day and prior to discharge from the CRU.
- Counsel on need to avoid alcohol, drugs, tobacco and medications throughout the study.
- Counseling on avoidance of pregnancy.

7.6 Follow-up – GROUP 4

Clinic Visit 02, Day 2

- Vital signs including oral temperature, blood pressure, and pulse will be obtained.
- A targeted physical exam may be performed, if indicated.
- Review concomitant medications
- Review for AEs and SAEs
- Draw 10 mL of blood for oxfendazole level -approximately 24 hours after dosing on day 1 (+/- 4 hours)
- Counsel on need to avoid alcohol, drugs, tobacco and medications throughout the study.

Clinic Visit 03, Day 4

- Vital signs including oral temperature, blood pressure, and pulse will be obtained.
- A targeted physical exam may be performed, if indicated.
- Review concomitant medications
- Review for AEs and SAEs
- Collect 15 mL of blood for safety panels (hemoglobin, white blood cell count, including neutrophil and eosinophil counts, platelet count, INR, partial thromboplastin time, Na, K, Cl, CO₂, blood urea nitrogen, creatinine, ALT, AST, and total bilirubin).
- Collect urine for dipstick testing for protein and glucose.
- Remind subjects to remain fasting (water is permitted) for 8 or more hours prior to study visit 04.

-
- Counsel on need to avoid alcohol, drugs, tobacco and medications throughout the study.

Clinic Visit 04, Day 8 (+/- 1 day)

- Vital signs including oral temperature, blood pressure, and pulse will be obtained.
- Review inclusion/exclusion criteria (including assessment of time of last oral food intake).

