- Perform a urine pregnancy test for females of childbearing potential.
- A targeted physical exam may be performed, if indicated.
- Review concomitant medications
- Review for AEs and SAEs
- A heparin lock will be inserted, blood will be drawn (10 mL) for baseline PK (prior to product administration)

Administration of Study Medication

A study nurse will administer a single 3 mg/kg oral dose of oxfendazole to the subject.

- For subjects who fasted during the first day of study drug administration, provide high fat breakfast prior to study drug administration. Approximately 30 minutes (+/- 15 minutes) following completion of the meal, the study nurse will administer a single 3 mg/kg oral dose of oxfendazole.
- For subjects who received a meal prior to the first day of study drug administration, subjects should fast for 8 hours prior to receipt of study drug and remain fasting (water is permitted) for two hours after the administration of drug.
- Lunch and dinner will be provided. Subjects will be allowed to eat snacks but will be asked to avoid drinking grapefruit juice and excessive (>2 cups) coffee.
- 10 mL of blood for oxfendazole level will be drawn at 30 minutes, 1, 2, 3, 4, 6, 9, and 12 hours (all times have a window of +/- 15 minutes except the 9 and 12 hour samples which have a window of +/- 30 minutes- it is critical to record the exact time of blood draw).
- Perform EKG approximately 2 hours following study drug (+/- 20 minutes)
- Assess AEs and SAEs throughout the day and prior to discharge from the CRU.
- Counsel on need to avoid alcohol, drugs, tobacco and medications throughout the study.
- Counseling on avoidance of pregnancy.

Clinic Visit 05, Day 9: (or 1 day following second dose)

- Vital signs including oral temperature, blood pressure, and pulse will be obtained.
- A targeted physical exam may be performed, if indicated.
- Review concomitant medications
- Review for AEs and SAEs

-
- Draw 10 mL of blood for oxfendazole level -approximately 24 hours after dosing on day 8 (+/- 2 hours)
 - Counsel on need to avoid alcohol, drugs, tobacco and medications throughout the study.

7.7 Final Study Visit 06 Day 14 (+/- 2 days) - GROUP 4

- Vital signs including oral temperature, blood pressure, and pulse will be obtained.
- A targeted physical exam may be performed, if indicated.
- Review concomitant medications
- Review for AEs and SAEs
- Draw 10 mL of blood for oxfendazole level

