11.1 Study Hypotheses

The primary objective of this study will be assessed through estimation rather than hypothesis testing, as this is a Phase I study with small sample sizes. The study includes eight subjects in each of the first three cohorts and twelve subjects in the fourth cohort.

The secondary objective of defining the multi-dose kinetics of oxfendazole will be assessed using a descriptive analysis with no formal hypothesis test. For the secondary objective of the determination of the effect of food on the kinetics of oxfendazole, equivalence between the fasting (water is permitted) and fed conditions will be tested using 90% confidence intervals and 80-125% equivalence limits for AUC_{0-∞}, AUC₀₋₂₄, and C_{max} in accordance with FDA guidance.

<http://www.fda.gov/downloads/RegulatoryInformation/Guidances/UCM126833.pdf>

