2.2. Dose Administration

In the first phase of the study, subjects will be administered oxfendazole q24 hours via oral syringe by a study nurse or investigator on Days 1, 2, 3, 4 and 5. Subjects will be fasting (water is permitted) for 8 hours prior to, and for 2 hours after, the administration of drug

In the second phase, half of the subjects will receive a single dose of 3 mg/kg of oxfendazole following an 8 hour fast and the other half will receive a single dose following a high fat meal. After 7 days, each subject will cross over to receive a single dose of oxfendazole (3mg/kg) following either a high fat meal or following an 8 hour fast. Subjects receiving a high fat meal will be administered study product approximately 30 minutes (+/- 15 minutes) following completion of the meal. Subjects who fasted prior to receiving study product will remain fasting for 2 hours after administration of drug. Lunch and dinner will be provided. Subjects will be allowed to eat snacks but will be asked to avoid drinking grapefruit juice and excessive (>2 cups) coffee.

Subjects in both phases of the study will be provided lunch and dinner on day of dosing. If vomiting occurs following ingestion of the study product, that dose will not be replaced. All subjects will be counseled to avoid drug, alcohol, and tobacco use through the end of the study.

Additional details regarding study product administration can be found in the protocol and Manual of Procedures (MOP).

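### In Group 4 the fasted condition is protected from food only to 2 hours after dosing, the reported median Tmax, and later food is neither timed nor matched between periods, so some dilution of the fed/fasted ratio toward 1 cannot be excluded.

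*Protocol*

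**What the plan says.** The fasted condition in Group 4 is an 8-hour fast before the dose plus a short fast after it. For Day 1, Protocol 7.5 says "Fasting (water is permitted) subjects will remain fasting (water is permitted) for two hours after the administration of drug". For Day 8, Protocol 7.6 has the crossed-over subjects "remain fasting (water is permitted) for two hours after the administration of drug". SAP 2.2 agrees: "Subjects who fasted prior to receiving study product will remain fasting for 2 hours after administration of drug". No post-dose fast is set for the fed condition.

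On later food, Protocol 7.5 and 7.6 say: "Lunch and dinner will be provided. Subjects will be allowed to eat snacks". Grapefruit juice and excess coffee are restricted, but no clock time, content or matching between periods is given. Neither section asks for the time of the first post-dose food to be recorded, although both stress exact blood-draw times.

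On absorption, Protocol 2.1.2 reports from the earlier single-dose study (0.5-60 mg/kg): "The median time of maximum concentration (T_{max}) occurred at 2 hours". The half-life "was consistent between groups and ranged from 8.5-11 hours". Protocol 2.1 adds that the drug "reaches peak blood levels more slowly following absorption from the intestinal tract than many other benzimidazoles", without giving a rate.

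On the analysis, Protocol 11.1 says equivalence of fed and fasted conditions "will be tested using 90% confidence intervals and 80-125% equivalence limits". SAP 3.5.7 applies this to AUC to infinity, AUC to the last measurable concentration, and Cmax.

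**The concern.** The post-dose fast is part of what defines the fasted treatment, so it belongs to the quantity that the food objective estimates. If the median Tmax is 2 h, up to half of subjects may peak after eating becomes permitted. In those subjects some of the fasted-period dose could be absorbed in the presence of food.

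If that food acts on unabsorbed drug as the pre-dose high-fat breakfast does, the two conditions become more alike and the ratio shrinks toward 1. In a superiority comparison such dilution would be conservative. In an equivalence test it makes a wrong conclusion of no food effect more likely.

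Because post-dose food is neither fixed nor recorded, any dilution could not be measured or adjusted for afterwards. Variable snack times may also add within-subject noise. The documents give no figure for that noise, but the stated power is sensitive to it, falling from 80% at CV 0.175 to 64% at CV 0.20.

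**Working it through.** **1. The plan's own power figure.** Inputs from Protocol 11.1 and 11.2: n = 12, 2x2 crossover, 90% CI (two one-sided tests at 0.05), limits 0.80-1.25. The true ratio is not stated and is taken as 1.00. On the log scale, sigma = sqrt(ln(1 + CV^2)), SE = sigma x sqrt(2/12), df = 10. Exact power is 79.9% at CV 0.175 and 64.4% at CV 0.20, against 80% and 64% stated. The figure reproduces, and the same calculation is used below.

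**2. Share not yet absorbed at 2 h.** Assumptions: one compartment, first-order absorption faster than elimination. Elimination rate ke = ln(2)/half-life, which is 0.0815 per hour at 8.5 h and 0.0630 at 11 h. The absorption rate ka solves Tmax = ln(ka/ke)/(ka - ke). The unabsorbed share is u = exp(-2 ka). The 3 h and 4 h values of Tmax are illustrations; the documents give only the median.

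**3. Diluted ratio for one subject.** Suppose food is eaten at exactly 2 h and acts on all remaining drug as fully as the pre-dose breakfast. The fasted AUC is then multiplied by (1 - u) + uR, and the observed ratio is R/(1 + (R - 1)u). With R = 1.30:

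| Subject's Tmax | ka (per h) | u | Observed ratio |
|---|---|---|---|
| 2 h | 1.56-1.72 | 0.03-0.04 | 1.283-1.288 |
| 3 h | 0.87-0.98 | 0.14-0.18 | 1.235-1.247 |
| 4 h | 0.57-0.64 | 0.28-0.32 | 1.185-1.201 |

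Each range runs from half-life 8.5 h to 11 h, except that u falls as half-life rises.

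**4. Trial-level ratio.** With a median Tmax of 2 h, at most half of subjects can peak later, so the 3 h and 4 h rows cannot describe the whole group. With the other half at 2 h, the geometric mean is the square root of the product of two rows. At half-life 8.5 h with half at 3 h, sqrt(1.283 x 1.235) = 1.259. The chance of declaring equivalence when the true ratio is 1.30 (n = 12, CV 0.175) is then:

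| Scenario | Trial-level ratio | False equivalence |
|---|---|---|
| No dilution | 1.30 | 1.5% |
| All at Tmax 2 h | 1.283-1.288 | 2.1-2.3% |
| Half at 3 h | 1.259-1.267 | 3.4-4.1% |
| Half at 4 h | 1.233-1.243 | 5.8-7.1% |

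These figures are for a single AUC parameter.

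**5. Cmax.** A fasted peak reached by 2 h cannot be changed by food eaten later. Only subjects who peak after 2 h could have Cmax affected, and their number at 3 mg/kg is not given.

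**6. The extreme case, for comparison.** If absorption were slower than elimination, so that it set the observed half-life, u = exp(-2 ke) = 0.85-0.88 and a ratio of 1.30 would read 1.03-1.04.

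**The case against.** The strongest reply is that Tmax marks the moment when input equals elimination, and that at the only Tmax the documents give, a 2-hour fast already covers about 96% of absorption. The AUC ratio then moves by about 1%. That stands.

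It also stands that 2 h is when eating becomes permitted and is not a scheduled meal, and that a later snack may do less than a high-fat breakfast finished about 30 minutes before the dose. If later food has no effect, there is no bias. The figures above are therefore upper bounds on the food action for each Tmax pattern shown.

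A reader might infer something stronger: that later absorption does happen with food in both periods, so that the ratio is definitely pulled to equivalence. The documents do not support that. They do not say when anyone eats, how much drug is absorbed by 2 h, or how later food acts.

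A reader might also take the absorption-limited case in step 6 as a live possibility, since Protocol 2.1 describes slow attainment of peak levels. That statement is a comparison with other benzimidazoles and carries no rate. The plateau in exposure reported in Protocol 2.1.2 is at 15 mg/kg, while Group 4 receives 3 mg/kg. No figure in the documents points to absorption-limited elimination.

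What the reply leaves unanswered is that neither document justifies 2 h against an absorption profile, and that later food is uncontrolled and unrecorded.

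**Conclusion.** The point holds as a modest design weakness. The fasted reference is protected only to the median Tmax, and the food that follows is not matched between periods. Any resulting bias would most plausibly run toward 1, which is the wrong direction for an equivalence claim. That direction is conditional on later food acting as the pre-dose meal does.

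For a true AUC ratio of 1.30, the observed ratio would be about 1.285 if all subjects have Tmax 2 h and about 1.23-1.27 if half peak at 3-4 h. False equivalence would rise from 1.5% to about 2-7% at CV 0.175. This rests on the one-compartment model, a half-life of 8.5-11 h, food acting fully from 2 h, and no subject peaking later than 4 h. The earlier study's median covers several dose levels, and its prandial state is not reported, so its transfer to fasted subjects at 3 mg/kg is also an assumption.

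**What to change.** In Protocol 7.5 and 7.6 and SAP 2.2, for Group 4 only:

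- Give the first and all later post-dose meals and snacks at the same fixed post-dose times and with the same content in both periods.
- Record the actual times.
- Place the first post-dose food after the expected absorption peak. The sponsor should choose and justify the time from the individual concentration-time data of the earlier single-dose study. No particular duration is proposed here, because the documents give no absorption profile from which to derive one.

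Leave Groups 1-3 as they are. They contain no food contrast, and SAP 3.5.3 compares Day 5 with Days 3 and 4 to judge steady state. Changing the fast on only some dosing days would mix that comparison with a change in feeding conditions.

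The cost is a somewhat longer time without food on two days when subjects are already in the unit for the 12-hour sample, plus wording in both documents and one more item to record.

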7.8 Early Termination Visit

If a subject withdraws from the study early, the following procedures should be performed at the early termination visit.

- Review current health status (interim medical history) and note any changes since the last visit
- Review concomitant medications
- Vital signs including oral temperature, blood pressure, and pulse will be obtained.
- Blood and urine will be collected for safety laboratory tests
- Blood will be obtained for PK studies
- A targeted physical examination may be performed, if indicated.
- Information regarding AEs and SAEs will be solicited. Any ongoing AEs or SAEs will be followed to resolution or until a stable chronic condition has been established.

Follow-up assessments will be completed according to the protocol schedule, if possible.

7.9 Unscheduled Visit

Unscheduled visits may occur at any time during the study. Unscheduled visits may occur after the scheduled final study visit (Day 10 or 14, depending on Study Group) if necessary to follow any AE occurring during the study period to resolution or stability. The procedures below are to be performed at any unscheduled visit. See the Manual of Procedures (MOP) for instructions on documentation and data reporting.

- Interim medical history will be reviewed.
- Review concomitant medications.
- Vital signs (P, BP, oral T), if clinically indicated will be obtained.

-
- A targeted physical exam, if indicated based on symptoms will be performed.
 - Adverse events and serious adverse events will be reviewed.

8 STUDY PROCEDURES/EVALUATIONS

8.1 Clinical Evaluations

Medical History: Will be obtained by interview of the subjects. Subjects will be queried regarding a history of significant medical disorders of the head, eyes, ears, nose, throat, mouth, cardiovascular system, lungs, gastrointestinal tract, liver, pancreas, kidney, nervous system, blood, lymph glands, endocrine system, musculoskeletal system, skin, and genital/reproductive tract. A history of any allergies, cancer, immunodeficiency, psychiatric illness, substance abuse, and autoimmune disease will be solicited.

Interim Medical History: Will be obtained by interview of the subjects. Subjects will be queried regarding new signs or symptoms that have occurred since the screening medical history was obtained.

Concomitant Medications: All current medications and medications taken in the 30 days before the screening visit (prescription and over-the-counter drugs) will be documented, as well as vitamins and supplements, and alternative/complementary medications through the last study visit. Assessment of eligibility also will include a review of prohibited medications (per the exclusion criteria).

Physical Examination: This examination will be conducted at Screening and Visit 1 and will assess general appearance including height and weight (at Screening only), vital signs (blood pressure, temperature, pulse), and the following areas/symptoms: skin, lymph nodes, head, eyes, ears, nose, throat, respiratory, cardiovascular, abdomen, extremities, musculoskeletal, and neurological.

Vital Signs and Targeted Physical Examination: Vital signs will be collected at each scheduled study visit and at the Early Termination Visit. Vital signs will be collected if indicated at the unscheduled visit. A targeted physical examination may be conducted at any study visit based on interim medical history.

Adverse Events Assessments: Subjects will be asked if they have any new symptoms since the prior visit. Please see section 9.2.1 and 9.2.2.

8.2 Laboratory Evaluations

8.2.1 Clinical Laboratory Evaluations

Clinical laboratory evaluations will be performed by the University of Iowa Clinical Pathology Laboratory.

Specific tests to be performed are described below:

Hematology includes: hemoglobin, WBC count, neutrophil count, platelets

Coagulation includes: INR and partial thromboplastin time

Clinical chemistry includes: Na, K, Cl, CO₂, blood urea nitrogen, creatinine, ALT, AST, total bilirubin

Serology: HIV 1/2 antibody, hepatitis B surface antigen (HBsAg), and hepatitis C virus (HCV) antibody

Urinalysis will be performed by dipstick testing for proteinuria and glucose in the research clinic. Confirmatory testing may be sent to the University of Iowa Clinical Pathology Laboratory for reflectance spectrophotometry analysis. Note: Urinalysis may be deferred if a participant is menstruating, but should be performed as soon as possible.

Urine Pregnancy Test: will be performed at screening and Day 1 in females of child bearing potential for all groups.

EKG: will be performed in the research clinic by research personnel trained in EKG administration. EKG tracings will be interpreted by a board certified cardiologist.

One or more of the laboratory parameters may be repeated at any time during the study as determined by the PI, if indicated by an AE. A clinically significant abnormal value should be repeated within 10 days if possible and followed up as clinically relevant.

